6.5 Suspension or Early Termination

Early Termination is the closure of a clinical study that occurs prior to meeting defined endpoints. This

is possible for the whole study or a single site. Suspension is a temporary postponement of study activities related to enrollment and distribution of the product. This is possible for the whole study or a single site.

6.5.1 Study-wide Suspension or Early Termination

Possible reasons for considering study suspension or termination of the study include but are not limited to:

[figure not shown]
- Observed/suspected performance of study app different from the original intent
- Decision by Medtronic or regulatory body (where the study is operating under regulatory body authority)

6.5.2 Investigator/Site Suspension or Early Termination

Possible reasons for clinical investigator or site termination or suspension include but are not limited to:

- Failure to obtain initial IRB approval or annual renewal of the study approval
- Lack of enrollment
- Noncompliance to regulations and the terms of the Clinical Trial Agreement (e.g., failure to submit data in a timely manner)
- IRB suspension of the site

Version: 2.0 29 JUL 2022

Page 16 of 17

- Fraud or fraudulent misconduct is discovered (as defined by local law and regulations)
- Investigator request (e.g., no longer able to support the study)

6.5.3 Procedures for Suspension or Early Termination

Below procedures will apply in addition to any other specific requirement per local regulations.

Medtronic-initiated and regulatory authority-initiated

[figure not shown]
- Medtronic will promptly inform the clinical investigators of the termination or suspension and the reasons and inform the regulatory authority(ies) where required
- In the case of study termination or suspension for reasons other than a temporary EC approval lapse, the investigator will promptly inform the EC. A detailed written explanation of the termination or suspension will be provided, where required per regulatory requirements
- In the case of study termination, Medtronic will inform the subjects via the study app.
- In the case of a study suspension, subject enrollment must stop until the suspension is lifted by Medtronic.
- In the case of a study suspension, enrolled subjects should continue to be followed out of consideration of their safety, rights, and welfare

Investigator-initiated

- The investigator will immediately or promptly inform Medtronic and provide a detailed written explanation of the termination or suspension (Medtronic, in turn, will notify affected patients via the study app)
- The investigator will promptly inform the institution (where required per regulatory requirements)
- The investigator will promptly inform the EC, along with a detailed written explanation of the termination or suspension (where required per regulatory requirements)
- In the case of a study suspension, subjects enrolled should continue to be followed out of consideration of their safety, rights, and welfare

IRB-initiated

Version: 2.0 29JUL2022 Page 17 of 17

- The investigator will inform Medtronic and provide a detailed written explanation of the termination or suspension within 5 business days, or sooner if required per local requirements
- · Subject enrollment must stop until the suspension is lifted
- Subjects already enrolled should continue to be followed in accordance with EC policy or its determination that an overriding safety concern or ethical issue is involved
- The investigator will inform his/her institution (where required per local requirements)
- The investigator will promptly inform Medtronic, who will in turn inform the subjects via the study app with the rationale for the study termination or suspension to ensure appropriate care and follow-up is provided

7. Version History

Version	Summary of changes	Author(s)/Title
1.0	Not Applicable, New Document	[name], Principal Clinical Research Specialist
2.0	 Removal of CHA2DS2-VASc1 score from inclusion criteria Removed reference to requirement of Financial Disclosures since study is not following 21 CFR part 54 — administrative error it was included 	[name], Principal Clinical Research Specialist

iOS	iPhone Operating System (Apple's mobile operating system developed and distributed by Apple Inc. required for use of it's devices).			
IRB	Institutional Review Board			
LMM	Linear mixed model			
MDT	Medtronic			
ML	Machine Learning			
NPV	Negative predictive value			
PPV	Positive predictive value			
QoL	Quality of Life			
RDC	Remote data capture			
SAE	Serious Adverse Event			
SAP	Statistical Analysis Plan			
SME	Subject- Matter Expert			
TIA	Transient Ischemic Attack			
WAIC	Widely Applicable Information Criterion / Watanabe-Akaike Information Criterion			

Introduction 3.

This Statistical Analysis Plan (SAP) has been designed to document, before data are analyzed, the rationale for the study design, and the planned analyses that will be included in study reports. This SAP

Revision [2.0]

Page 4 of 25

does not limit the analysis in reports. Additional analysis of the study data beyond this plan may be needed. This SAP is developed for the DEFINE AFib study, based on the Clinical Investigation Plan (CIP) version 4 dated July 29, 2022.

Atrial fibrillation (AF) is the most frequent clinically significant cardiac arrhythmia. When diagnosed clinically, AF is associated with increased risk for stroke, heart failure (HF), cardiovascular (CV) morbidity and mortality. It is also a major contributor to the costs of health care. The prevalence of AF is predicted to rise significantly in the coming years due to the aging of the population and growing frequency of other AF risk factors. Considering the rising burden and clinical sequalae of AF, strategies that enable early detection and appropriate clinical management are needed.

Insertable cardiac monitors (ICMs) now allow for continuous arrhythmia monitoring for up to five years. These devices have enabled early detection of AF that can be asymptomatic, infrequent, and/or of short duration. Accordingly, AF detected by ICMs may not be diagnosed through traditional clinical assessment. Studies have demonstrated significantly higher rates of AF detection with ICM versus conventional monitoring in patients with a recent cryptogenic stroke (Sanna et al. 2014) and in patients undergoing catheter ablation for AF (Kapa et al. 2013). Moreover, four recent trials have observed high rates of AF detection (21%- 40% over 12-30 months of follow-up) with ICM monitoring in patients who have risk factors for AF and stroke, but no clinical history of AF. Two of these studies required conventional cardiac monitoring at baseline. Together these studies demonstrate that continuous monitoring with an ICM can identify AF that would not be readily detected through standard clinical assessment.

Prior studies have demonstrated that device-detected AF is associated with the same clinical outcomes as AF diagnosed through standard clinical practice, including stroke, mortality, and heart failure. However, AF detected on implantable cardiac devices including ICMs can be transient and short in duration. The amount of device-detected AF required to increase the risk of cardiovascular morbidity and mortality is unclear. Prior studies have observed device-detected AF of different thresholds ranging from 6 minutes to 24 hours is associated with an increased risk of stroke. While stroke risk seems to increase with longer durations of device-detected AF, this relationship is not linear, and is impacted by the presence of other stroke risk factors. Even less evidence is available for other adverse consequences of AF such as mortality, healthcare utilization and quality of life. Accordingly, physicians are not clear when or how to intervene when AF is detected by ICM monitoring. A key requirement to advance the management of AF patients is the development of tools that can assess important variables such as AF burden or patterns of AF that, alone or in combination with other clinically important variables, improve the risk prediction for AF-associated clinical outcomes with greater efficacy than current risk stratification modalities. Therefore, the purpose of this study is to evaluate the association between complex patterns of device-detected AF and elevated healthcare utilization, reduced quality of life (QoL) and specific clinical outcomes in patients with a LINQ ICM. These data will improve our understanding of how data from the LINQ ICM can be used to guide the management of patients with AF.

DEFINE AFib Statistical Analysis Plan Form Medtronic Revision [2.0] Page 5 of 25

[figure not shown]
Study Objectives

4.1 Primary Objective

To evaluate whether summary and episodic measurements collected by market-released LINQ ICMs are able to predict increased AF-related healthcare utilization (HCU)

Endpoint: Confirmed healthcare visit in the inpatient hospital, outpatient hospital, clinic/office, emergency department, or other care location (including remote visits) where AF was a reason or suspected reason for healthcare interaction

[figure not shown]
Investigation Plan 5.

DEFINE AFib is an observational, post-market clinical study intended to leverage machine learning to evaluate the association between complex patterns of device-detected AF and elevated healthcare utilization, reduced QoL and specific clinical outcomes in patients with a LINQ ICM. These data will improve the business understanding of how data from the LINQ ICM can be used to guide the management of patients with AF.

This study is expected to be conducted at approximately 30 centers in the United States, and it will enroll approximately 5,000 patients (see section 13.1 of the CIP). Study subjects will be followed for up to 5 years, until study closure, or until their LINQ ICM either completes its service life or is explanted, upon which time they will no longer be followed. Study closure may occur when Medtronic requirements have been satisfied per the CIP and/or following a decision by Medtronic or applicable external parties (i.e. institutional review board (IRB) or regulatory authority) to discontinue the study.

Revision [2.0]

Page 7 of 25

Enrollment is anticipated to last for up to 3 years. The estimated total study duration is up to 7 years, representing a three-year enrollment period and up to 5 years of follow-up for all patients.

Inclusion Criteria

- Patients with a Reveal LINQ or LINQ II ICM who have a self-reported history of AF and who have received an ICM for the following device logged indications, categorized into the following groups:
 - o **Stroke**: Cryptogenic stroke indication
 - o **AF management**: AF management and post-ablation management indications
 - Suspected AF: Suspected AF and palpitations indications
- Individual access and ability to use an Apple iPhone® compatible with Medtronic's research app (iOS v. 13.X or higher)
- Patient is willing and able to comply with the protocol, including CareLink transmissions (requires
 adequate connectivity), remotely administered instructions, and remote survey participation
- Patient is 22 years of age or older
- Located in the United States, with CareLink managed through servers located in United States (50 states or District of Columbia)
- Valid email address self-reported at enrollment
- Patient must be able to read and write in English
- ICM device managed by a physician who is part of a participating network/clinic

Exclusion Criteria

Patients with > 24 months elapsed time from recorded LINQ ICM implant or > 48 months elapsed from recorded LINQ II ICM implant date.

Data Collected

The following data will be collected passively through Medtronic's research app. Data will be collected on an ongoing basis following documented patient consent, and until study termination or patient withdrawal. Following consent, patients will create a profile, opt in to sharing location, Electronic Health Record (EHR) data and other optional components of the study and the patient will have the opportunity to change data permissions that determine collectable data throughout the study. If patients consent to sharing their EHR data, that patient's EHR data will be pulled via the Apple Health app or through direct access to servers at each patient's site of service when available.

Electronic Health Records

- Clinical Vitals
- Diagnoses/Conditions
- Lab results
- Medications

Revision [2.0]

Page 8 of 25

- Medical procedure/clinical actions
- Patient mortality
- Health app data (when available, including but not limited to)
 - Steps counts to assess activity
 - Nutrition
 - o Sleep
 - o Vitals
 - Glucose
 - **Blood pressure**
 - SPO₂
 - o Body measurements
 - Weight
 - Height
 - Body mass index
- Location services (when available)
 - o Anonymized geofencing triggers

Patient surveys will be administered to assess QoL, HCU, changes in medical management, AFassociated symptoms, and medication use (see Table 1).

Table 1: Survey and Profile Update Cadence

•	Survey Category	•	Survey	•	Survey Type	•	Deployment Prerequisites	٠	Rules	•	Expiration
Medical History		•	Patient history	•	Static	•	eConsent completed	•	Only completed once at joining of study, necessary for enrollment	•	No expiration
		•	Medication history (MDT developed tool)	•	Static	•	eConsent completed	٠	Completed at beginning of study, available to update/modify over study timeline	•	No expiration
•1	Quality of Life	•	EQ-5D-5L	•	Static	•	eConsent completed	•	Starting at enrollment and then every 3 months (every 90 days +/-2 days**)	•	30 days post issuance
		•	AFEQT	•	Static	•	eConsent completed	•	Starting at enrollment and then monthly (every 30 days +/- 2 days**)	•	14 days post issuance

Revision [2.0]

Page 9 of 25

[figure not shown]
Healthcare Utilization	• HCU	Dynamic	Starting 30 days after enrollment or first triggered event	Starting 30 days after enrollment and then monthly (30 days +/-5 days*) (+/-2days**) (For triggered surveys, including healthcare facility geofence and daily AF burden from CareLink, consult CIP for details) HCU survey should always be deployed with Symptom and Symptom Severity Survey	7 days post- issuance
Symptom and Symptom Severity	MAFSI and modified EHRA symptom severity	Dynamic	Starting 30 days after enrollment or first triggered event	Starting 30 days after enrollment and then monthly (30 days +/- 5 day*)(+/-2days**) (For triggered surveys, including healthcare facility geofence and daily AF burden from CareLink, consult CIP for details) Symptom and Symptom Severity survey should always be deployed with HCU survey	7 days post issuance
Medication	• SMAQ	Static	• Starting 90 days after enrollment (+/-2 days**)	 Starting 90 days after enrollment and then every 3 months (every 90 days +/-2days**) 	30 days post- issuance
• Patient App	Patient impact	Static	Starting 6 months after enrollment (180 days +/- 2 days**),	Starting 6 months after enrollment and then every 6 months (every 180 days +/-2 days**)	90 days post- issuance

6. Determination of Sample Size

A retrospective analysis of the Optum EHR deidentified database (2007-2019), linked to the Medtronic CareLink database of insertable cardiac monitoring (ICM) devices, suggests that in a cohort of 5,000 patients from the intended population of ICM patients, 600 (12%) will have at least one ischemic stroke event and 2,350 (47%) will have at least one healthcare utilization in a five-year follow-up period. Of the healthcare utilization events, 1,050 (21%) will be AF-related. It is expected there will be approximately 5.2 million follow-up days. Given the large number of follow-ups, the ratio of events to follow-up days is extremely rare. Traditional classification approaches (CART, random forest) require under/oversampling

Revision [2.0]

Page 10 of 25

methods and control parameters for adequate convergence. In the retrospective analysis, the target window was defined as the five days prior to an event (thereby over-sampling events by a factor of five) and then under-sampled controls to a 1:1 ratio with over-sampled cases to create a balanced data set. Setting a minimum node size of 80 patients and requiring the minimum node size to range between 2% and 5% of balanced data, adequately converged to results. The undersampling and model fitting exercise were repeated 100 times to bootstrap an estimate of variable importance for each variable in the model. Using this methodology for convergence and estimation, a minimum of 160 (80/0.05/10) to 400 (80/0.02/10) events are needed for analyzing predictor variable influence and 320 to 800 events for creating a prediction algorithm that requires training, validation, and test partitions as part of its methodology. This latter range is sufficient for deep learning approaches (e.g., LSTM autoencoder, CNN classification network) for predicting extremely rare events.

A minimum of 320 to 800 events implies a 5,000 patient cohort is minimally sufficient for algorithm development. This, however, assumes patients enroll immediately after implant and does not consider attrition. Moreover, this analysis showed that 30% of patients will miss at least 50% of their daily CareLink transmissions. Considering these challenges, it is reasonable to expect as little as 50% of our cohort to provide complete data. In such a scenario, a 5,000 patient cohort would be sufficient for modeling health care utilization (1,175 events, 525 AF-related) but would be insufficient for modeling ischemic stroke or for modeling outcome events by smaller subgroups.

7. Statistical Methods

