7.9.1 Primary Objective

The primary objective require development of risk-prediction models for various endpoints using different data source combinations. This section describes a general framework that will be used to develop these models.

Prediction models

For each endpoint, two types of prediction modeling will be considered: one focusing on short term predictions and other on long term predictions. For both prediction modelling types, the following machine learning (ML)/artificial intelligence (AI) methods might be considered (but not limited to):

- Tree Boosting
- Temporal Convolutional networks feedforward neural network (TCN FFNN) (similar approach presented in Catling & Wolff (2020))

Dataset split

DEFINE AFib Statistical Analysis Plan Revision [2.0] Page 14 of 25 Medtronic

Predictive modelling requires the original data to be split into three smaller sets, one for training, one for validation and one for testing. The original data will be randomly split into those three datasets with 70%, 10% and 20% of patients in the training, validation, and testing datasets, respectively. A patient will only contribute data to one of the 3 datasets. To reduce impact of possible heterogeneity across sites, patients and LINQ model, randomization will be stratified by sites, LINQ indication, and LINQ model. Lastly, the testing dataset will only be used after the models under consideration have been trained and validated.

Data format

All predictive models will be trained using similar labeled examples. In particular, at a prediction time point **t** a patient **i** generates a labeled example (hereinafter referred as sliding window) which will be composed of the all features considered as relevant to the clinical endpoint (e.g. LINQ device data, EHR data, etc.) collected between **(t-b)** and **t**, and a binary label indicating if that patient had the clinical event of interest between time points **t+l** and **(t+l+w)**. Figure 1 illustrates the sliding window concept at time **t**. Notice a patient will provide multiple sliding windows.

[figure not shown]

Figure 1: A sliding window at time t is composed of all relevant features values observed from the most recent b days and a binary label indicating if event occurred between t+l and t+l+w. The rationale of the parameter l is to give leading time to the physicians to prevent an event for a patient with high risk of having that event between t+l and t+l+w

Data transformations

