After all models have been trained and tuned, all final models (i.e. for each clinical endpoint and prediction modeling strategy) will be fitted to the testing dataset resulting in a prediction of each patient's individual probabilities of having the clinical event in the predictive window (i.e. between t+l and t+l+w). More specifically, all models will generate risk prediction (for the clinical event they were designed to predict) for each patient at each day (starting at the bth). The true binary values and the corresponding prediction risk scores will be used to compute the area under the receiver operating characteristic (AUROC), sensitivity, specificity, negative predictive value (NPV) and positive predictive value (PPV). Bootstrapping will be used to compute 95% CIs for these performance metrics.

For each outcome, the performance of the risk prediction models will be presented in contrast to the performance of comparable clinical practices. However, as a guideline, the following scale might be used to help choose the adjective to refer the performance of each model:

AUROC ≤ 0.5: fail

DEFINE AFib Statistical Analysis Plan Form Medtronic Revision [2.0] Page 17 of 25

0.5 < AUROC ≤ 0.6: poor

0.6 < AUROC ≤ 0.7: fair

[figure not shown]
0.7 < AUROC ≤ 0.8: good

[figure not shown]
0.8 < AUROC ≤ 0.9: great

[figure not shown]
AUROC > 0.9: excellent

[figure not shown]
Determination of Subjects/Data for Analysis

Subjects in the full analysis set who have completed all enrollment surveys will be included in the primary objective analysis. Subject follow up might be limited by lack of device information.

[figure not shown]

[figure not shown]

DEFINE AFib Statistical Analysis Plan Form Medtronic Page 20 of 25 Revision [2.0]

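### SAP 7.9.1 reports one pooled AUROC per model over all daily windows, so recognising a recent AF-related visit cannot be told apart from prediction by LINQ measurements

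*SAP*

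**What the plan says.** The endpoint in SAP 4.1 is a confirmed visit, in any care setting, with AF as a reason or suspected reason. It is not limited to a patient's first such visit. Under Data format in SAP 7.9.1, a window at day t takes features from the preceding b days and is positive if the event falls between t+l and t+l+w. The SAP adds: "Notice a patient will provide multiple sliding windows". EHR data are named there as an example of a feature source, and SAP 5 lists diagnoses, medications and procedures among the EHR items collected.

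Under Tuning, b, l and w are chosen by grid search to maximise validation AUROC. Under Testing, each model gives a risk "for each patient at each day (starting at the bth" day), and AUROC, sensitivity, specificity, NPV and PPV are computed from those predictions. The released text does not stop a patient's windows at a first visit, say how repeat visits are treated, or report them separately.

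The sizing in SAP 6 and CIP 13.1 is worded differently. It states "2,350 (47%) will have at least one healthcare utilization in a five-year follow-up period", then "Of the healthcare utilization events, 1,050 (21%) will be AF-related". After an assumed 50% loss it calls the cohort "sufficient for modeling health care utilization (1,175 events, 525 AF-related"), and compares this with a need for "320 to 800 events for creating a prediction algorithm".

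**The concern.** The primary objective asks whether measurements collected by LINQ devices can predict AF-related HCU. An AF-related visit often leads to others, such as a follow-up, a procedure or a medication check. Where features include EHR entries, a model can raise a patient's risk because a visit has just been recorded, whatever the device shows. Windows that follow an earlier visit are then easy positives, and the pooled AUROC mixes two abilities: recognising that care is already under way, and anticipating a visit from device data.

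Only the second ability answers the objective. With a single pooled figure per model, a reader cannot tell how much comes from each. Tuning the look-back b to maximise AUROC can also favour values that capture recent visits.

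**Working it through.** **1. Sizing figures reproduced.** 0.47 × 5,000 = 2,350 and 0.21 × 5,000 = 1,050. Halved, these are 1,175 and 525. The requirement is 80/0.05/10 = 160 to 80/0.02/10 = 400, doubled to 320 to 800. All agree with the SAP. The alternative 0.21 × 2,350 = 494 does not give 1,050, so 21% is not a share of the 2,350. This suggests that 1,050 counts patients out of 5,000, although the sentence says events.

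**2. Inputs for the size of the effect.** From the documents: 5,000 patients; 5.2 million follow-up days, so 5,200,000/5,000 = 1,040 days each; 21% of patients with an AF-related visit. Assumed, because the documents give no value: the repeat-visit pattern, and b = 90, l = 7, w = 30 days.

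**3. Score tested.** The score is 1 if the patient had an AF-related visit in the last 90 days and 0 otherwise. It uses no LINQ data. For a binary score, AUROC = (sensitivity + specificity)/2.

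**4. Clustered visits (simulation).** Background visits are Poisson, or gamma-Poisson with shape 0.5 (frailty), set so that about 21% of patients have at least one. Each visit produces on average m further visits, 7 to 90 days later.

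| m | AUROC, no frailty | AUROC, frailty |
|---|---|---|
| 0.25 | 0.61 | 0.63 |
| 0.50 | 0.69 to 0.71 | 0.71 to 0.72 |
| 0.75 | 0.80 | 0.81 |

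Ranges show repeat runs. Windows after an earlier visit make up 31% to 72% of all positive windows.

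**5. Sensitivity to the assumptions.** With lags of 30 to 365 days, AUROC falls to 0.53 to 0.66. With b = 30, it is 0.55 to 0.71.

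**6. A different repeat model.** Here repeats occur at a constant rate after a first visit, without clustering.

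| Repeats per year | b = 90 | b = 180 | Any earlier visit known |
|---|---|---|---|
| 0.5 | 0.54 | 0.57 | 0.66 |
| 1 | 0.58 | 0.64 | 0.74 (0.735) |
| 2 | 0.66 | 0.74 | 0.82 |
| 4 | 0.75 | 0.84 | 0.87 |

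For example, at 4 per year and b = 90, (0.563 + 0.945)/2 = 0.754. At 1 per year, (0.200 + 0.964)/2 = 0.582.

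**7. Windows before a first visit.** If patients start with no visit history, the score is constant in these windows and its AUROC is exactly 0.50. With visits before follow-up added, it is 0.51 to 0.53 for a 90-day look-back and about 0.59 to 0.61 for a 1,000-day look-back.

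**The case against.** The strongest reply is that the plan does what its endpoint says. The endpoint is any AF-related visit and the objective is increased utilization, so repeats are legitimate events. This stands, and the pooled metrics should stay. A reader might infer that first visits are the true target and that the AUROC adjective should be based on them. Neither document says so, and the sizing never uses the word first.

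A reader might also infer that the model could be graded good without using LINQ data. That depends on an undocumented repeat rate, on b, l and w that are not yet fixed, and on features that reveal visits. CIP 13.3.1 names LINQ values and medical history given at enrolment; EHR data appear in SAP 7.9.1 only as an example. The AUROC bands are an optional wording guide, and no hypothesis is tested.

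The plan also has partial safeguards: comparison with clinical practice, different data-source combinations, and an error analysis of cohorts with higher prediction error. None of these separates windows by earlier visit.

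The split is not a clean separation either. All patients report a history of AF and may enrol up to 24 or 48 months after implant, so care before follow-up can still inform the windows before a first visit (step 7).

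Finally, a reader might infer from the mix of patients and events that the study is too small. It does not follow: if the counts are patients, repeats only add events. Some SAP pages are not in the released text, so a rule on repeats there cannot be excluded.

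**Conclusion.** The point holds as a gap in reporting. As written, a pooled AUROC from a model with visit-revealing features cannot show how much of its performance comes from LINQ measurements. A score with no device data reaches about 0.61 to 0.81 under 7-to-90-day clustering with a matching 90-day look-back, and about 0.53 to 0.71 when the lags are longer or the look-back shorter. These figures show what is possible under assumed repeat rates; they do not forecast this study. For models using device data alone the concern is weaker, since they do not see earlier visits directly.

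The sizing wording needs clarifying, but the adequacy of the sample size is not affected. This is a worthwhile, inexpensive improvement and does not call the design into question.

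**What to change.** In SAP 7.9.1 Testing, keep the pooled metrics for the any-visit endpoint. Add AUROC, sensitivity, specificity, PPV and NPV on the test set, with confidence intervals, separately for windows before and after the patient's first confirmed AF-related HCU in follow-up. Assign each window by its prediction day t; patients with no such visit contribute only to the first group. State that first means first in follow-up, because every patient has a history of AF. Interpret the pooled AUROC beside both groups, and leave the AUROC adjective on the pooled figure.

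In SAP 6 and CIP 13.1, state whether 2,350/1,175 and 1,050/525 are patients with at least one event or visits.

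The cost is a few lines of SAP text and one more split of predictions that will already exist. The downside is wider intervals within each group. If the sizing counts are patients, the 20% test set holds about 0.20 × 1,050 = 210 patients with an AF-related visit, or 0.20 × 525 = 105 after the assumed loss, and only these can contribute windows to the second group.
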